5.4. Methods to Manage Missing Data

Missing values will not be imputed in the analysis. However, in the event of extensive missing data, alternative imputation methods may be explored.

6. ANALYSES AND SUMMARIES

6.1. Primary Endpoint(s)

6.1.1. Percentage change from baseline to Week 13 in Urinary Protein to Creatinine Ratio based on 24-hour urine collection (UPCR)

6.1.1.1. Primary Analysis

The primary analysis will be based on the FAS. A MMRM approach as specified in Section 5.3.3 will be fit to the post-dose 24-hour urine collection data on UPCR (i.e. Weeks 5, 9 and 13). All UPCR values (including baseline) will be \log_e -transformed prior to analyses. The primary analysis will include the change from baseline values of UPCR (on the \log_e -scale) as the dependent variable.

Absolute values and percentage changes from baseline in UPCR (based on 24-hour urine collection) will be summarized descriptively by dose (if applicable) and timepoint as described in Section 5.3.3. Tables will present all Lead-in Period, baseline and post-baseline time points where applicable. All 24-hour urine collection data will be included in the data listings.

The probabilities for the decision criteria for each of the doses (as required) will be calculated directly from the results of the MMRM. These are the probabilities that the reduction from baseline due to PF-06730512 (each dose level) is greater than (i) 0% and (ii) 35%. The LSMeans at Week 13 will be used to derive the posterior probabilities associated with the decision criteria.

A table showing the estimate of the mean of the posterior distribution for the percentage change from baseline for each dose of PF-06730512 (if applicable), the 90% credible interval and the posterior probabilities of passing the decision criteria will be produced (Appendix 3).

The following results from the above primary analysis will be plotted:

- Individual profile plots of the raw values (including all time points from Week -8, to Week 33) against time. Two plots per dose will be generated of absolute values and percentage changes from baseline. To distinguish between subjects enrolled before and after amendment 5, assessments from each individual's Follow-up Period will be interpolated with a different line style (e.g., a dashed line) than assessments from the Investigational Treatment Period.
- Profile plots of the back-transformed LSMeans (including 90% confidence intervals) over time, with a separate line included for each dose (if applicable).

No imputation of missing values will be conducted and all available data through Week 13 will be used in the MMRM models.

6.1.1.2. Sensitivity/Robustness Analyses

The following sensitivity analyses to the primary endpoint will be carried out:

- CCI
[REDACTED]
- The primary efficacy endpoint will be analyzed for individual dose levels separately, and will follow the format described in section 5.3.3 and 5.3.4..
- The primary efficacy endpoint of % change from baseline in UPCR at week 13, and for all study weeks will be performed including the following potentially relevant covariates: GFR; disease duration (quantized into four categories);; and FSGS type, as measured by Columbia Classification consisting of the following categories: PERIHILAR, CELLULAR, COLLAPSING, NOT OTHERWISE SPECIFIED. In the event the model does not converge due to sparseness in FSGS type, for example, a modified model excluding sparse covariates that impact model performance will be performed.
- CCI
[REDACTED]
- CCI
[REDACTED]
- The primary analysis MMRM model described in Section 6.1.1.1 will be repeated using the associated PPAS.

6.1.1.3. Statistical Model Diagnosis

The presence of outliers will be investigated for the primary analysis. An outlier will be defined as any response data value with a studentized (conditional) residual greater than 3, or less than -3. A listing will be generated of any subjects meeting these criteria for diagnostic purposes. The assumptions of normality will be verified graphically using residual plots.

If there are outliers or major deviations from normality then the effect of these on the conclusions will be investigated through alternative transformations and/or analyses
[REDACTED]

excluding outliers. Justification for any alternative to the planned analysis will be given in the report of the study.

6.2. Secondary Endpoint(s)

6.2.1. Percentage change from baseline to Weeks 2, 5, 9, and beyond Week 13, as applicable, in Urinary Protein to Creatinine Ratio (UPCR)

The analysis methodology for this secondary endpoint is summarized in Section 3.2.1.

For the CSR, an additional summary statistic table will be provided that is based on the respective SAS population.

6.2.2. Percentage change from baseline to Weeks 3, 5, 9, 13 and beyond, as applicable, in estimated glomerular filtration rate (eGFR)

The analysis for this eGFR endpoint will follow the same type of MMRM model and descriptive summary statistics as the primary analysis model (Section 6.1.1). Additional details regarding the handling of the eGFR endpoint can be found in Section 3.2.2.

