2. STUDY OBJECTIVES AND ENDPOINTS

[figure not shown]
Primary Objective(s):	Primary Endpoint(s):

 To evaluate the efficacy of PF-06730512 compared to baseline in the reduction of proteinuria following 12 weeks of treatment in patients with FSGS. 	
 Percentage change from baseline to Week 13 in Urinary Protein to Creatinine Ratio (UPCR), calculated from the 24-hour urine collection.
Secondary Objective(s):	Secondary Endpoint(s):

 To evaluate the safety and tolerability of PF-06730512 following up to 24 weeks of treatment in subjects with FSGS. To evaluate the effects of PF-06730512 on proteinuria time course. To evaluate the effect of PF-06730512 on renal function. To evaluate the serum exposure of PF-06730512 in FSGS patients. To evaluate the immunogenicity profile of PF-06730512. 	
 Adverse Events, Laboratory Safety Tests (Hematology, Clinical Chemistry, Urinalysis), Body Weight, Blood Pressure, Pulse Rate, Body temperature and Electrocardiogram (ECG). Percentage change from baseline to Weeks 2, 5, 9, and beyond Week 13, as applicable, in UPCR. Percentage change from baseline to Weeks 3, 5, 9, 13 and beyond, as applicable, in estimated glomerular filtration rate (eGFR). Serum concentration of PF-06730512. Incidence of the development of anti-drug antibody (ADA) and neutralizing antibody (NAb).
CCI	

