9.2.2. Analysis of Secondary Endpoints

The secondary endpoints of percentage change from baseline in UPCR over time post-treatment will come from the same MMRM model used for the primary analysis using post-treatment data, including time points beyond Week 13 as applicable. Estimates of percentage changes from baseline to weeks post-treatment will be derived from a model similar to the primary MMRM model.

Changes from baseline to Weeks 3, 5, 9, 13 and beyond as applicable, in eGFR over time post-treatment will be analyzed using an approach similar to that used for the primary endpoint. This will also be analyzed on the \log_e scale.

Full details of these and all other secondary efficacy analyses will be included in the SAP.

CCI

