3.2. Secondary Endpoint(s)

3.2.1. Percentage change from baseline to Weeks 2, 5, 9, and beyond Week 13, as applicable, in Urinary Protein to Creatinine Ratio (UPCR)

The secondary efficacy endpoints include percentage change from baseline to Weeks 2, 5 and 9 in UPCR based on both the 24-hour urine collections and the first morning voids. All analyses and descriptive summaries will report first morning void assessments and 24-hour urine assessments of UPCR separately. Descriptive statistics will be used to summarize UPCR by dose and timepoint for all timepoints in the Lead-in Period and the Investigational Treatment Period, as well as Week 13 data for subjects enrolled prior to amendment 5 and Week 25 data for subjects enrolled after amendment 5.

For descriptive summaries, percentage change from baseline will be calculated for each post-baseline measurement based on the respective urine collection, as that measurement minus the baseline value divided by the baseline value multiplied by 100.

3.2.2. Percentage change from baseline to Weeks 3, 5, 9, 13 and beyond, as applicable, in estimated glomerular filtration rate (eGFR)

The secondary efficacy endpoints of percentage change from baseline in estimated glomerular filtration rate (eGFR) include Weeks 3, 5, 9 and 13. Descriptive statistics will be used to summarize eGFR by dose and timepoint for all timepoints in the Lead-in Period and the Investigational Treatment Period, as well as Week 13 data for subjects enrolled prior to amendment 5 and Week 25 data for subjects enrolled after amendment 5.

The eGFR will be calculated based on the Chronic Kidney Disease Epidemiology Collaboration (CKD-EPI) formula¹ (see Appendix 4).

Baseline is defined as the Week -1 measurement. If the Week -1 eGFR measurement is not available, the nearest eGFR measurement taken to the Week -1 visit will be used, provided it is pre-dose.

Log-transformed change from baseline will be the dependent variable in the analysis models. The percentage change from baseline will be calculated for each post-baseline measurement, as that measurement minus the baseline value divided by the baseline value multiplied by 100.

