4. ANALYSIS SETS

4.1. Full Analysis Set

The Full Analysis Set (FAS) is defined as all enrolled subjects who have received at least one dose of study treatment and have at least one post-baseline measurement of UPCR based on 24-hour urine collection.

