5.3. General Methods

5.3.1. Summary Analyses for Continuous Data

Continuous variables will be presented using summary statistics: number of observations, arithmetic mean, standard deviation, median, minimum and maximum values. For endpoints to be analysed on the natural log scale, the geometric mean and geometric coefficient of variation will additionally be calculated.

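### SAP 6.2.1 plans only observed-case summaries of UPCR at Week 2 and beyond Week 13, which conflicts with the model in Protocol 9.2.2 and with SAP 5.3.3

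*SAP*

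**What the plan says.** The endpoint in Protocol Section 2 is "Percentage change from baseline to Weeks 2, 5, 9, and beyond Week 13, as applicable, in UPCR". Protocol 9.2.2 says that the UPCR time course "will come from the same MMRM model used for the primary analysis using post-treatment data, including time points beyond Week 13 as applicable", and adds that the estimates may come from a model similar to the primary one.

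SAP Section 5 sends the reader to Sections 6.1 and 6.2 for the methods of the primary and secondary endpoints. For this endpoint, SAP 6.2.1 reads: "The analysis methodology for this secondary endpoint is summarized in Section 3.2.1". It adds one further summary table on the safety set. SAP 3.2.1 then states: "Descriptive statistics will be used to summarize UPCR by dose and timepoint for all timepoints in the Lead-in Period and the Investigational Treatment Period". It extends this to Week 13 for subjects enrolled before Amendment 5 and to Week 25 for those enrolled after it. SAP 5.3.1 lists the content of such summaries as "number of observations, arithmetic mean, standard deviation, median, minimum and maximum values", with geometric mean and geometric CV added for log-scale endpoints. SAP 5.4 says that missing values are not imputed.

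The primary MMRM in SAP 6.1.1.1 is fitted to 24-hour UPCR at Weeks 5, 9 and 13, with data through Week 13.

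**The concern.** A programmer who follows SAP 6.2.1 will produce tables of whoever has a value at each visit, with no model and no interval, at Week 2 and at every visit after Week 13. The protocol promises more than that. The visible change log in the SAP does not report the model as removed and gives no reason for removing it.

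Proteinuria time course is a secondary objective, and Amendment 5 extended treatment partly to look at durability of response. The study has no control arm, so a drift in the observed means caused by selective attrition could not be told apart from a sustained effect. With about 22 subjects per cohort, a point estimate without an interval also says little about how well durability has been measured.

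**Working it through.** **Passages side by side**

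| Place | UPCR at Weeks 5, 9 | UPCR at Week 2 and after Week 13 |
|---|---|---|
| Protocol 9.2.2 | MMRM | same or similar MMRM |
| SAP 5.3.3 (general) | MMRM, 90% intervals by week | MMRM, if the general statement is taken to apply |
| SAP 6.1.1.1 | in the primary MMRM | not included |
| SAP 6.2.1 and 3.2.1 | descriptive | descriptive only |
| SAP Appendix 1.1, secondary outputs (visible part) | summary table | no MMRM output |

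SAP 6.2.2 names an MMRM for eGFR, and Appendix 1.1 lists MMRM and LSMean outputs for it. The only UPCR row among the secondary outputs is a summary table by nephrotic-range group. SAP 6.2.1 does not refer to 5.3.3.

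**Size of a possible bias**

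The plan states no figure that could be reproduced. The documents do not show the SD of the log change or the dropout after Week 13, so both are assumed here.

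Inputs:
- 22 subjects (Protocol summary, approximate cohort size).
- True change of -35% at Weeks 13, 17, 21 and 25, chosen to match the second decision criterion in SAP 5.2.
- SD of log change 0.4, 0.6 or 0.8, with correlation 0.7 between visits (assumed).
- Dropout after Week 13 of 10%, 18% or 30% in total (assumed). The middle value borrows 1 - 18/22 = 18.2%, from about 18 of 22 subjects at the Week 13 assessment (Protocol 9.6).
- At each interval, dropout is logistic in the last observed value, with slope 1 or 2 per SD. Subjects doing worse leave more often (assumed).

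With 4,000 simulated trials per scenario, the Week 25 estimates were:

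| Dropout | Observed-case mean | Overstatement (points) | Likelihood (MMRM-type) |
|---|---|---|---|
| 10% | -36.8% to -40.5% | 1.8 to 5.5 | -34.9% to -35.2% |
| 18% | -38.0% to -43.9% | 3.0 to 8.9 | -34.9% to -35.2% |
| 30% | -40.2% to -48.6% | 5.2 to 13.6 | -34.9% to -35.2% |

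The likelihood estimate recovers the truth because the dropout was generated as missing at random. If dropout does not depend on UPCR, the observed-case bias is zero.

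**What the missing interval would show**

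The 90% interval for the ratio to baseline is 0.65 × exp(± t × SD/√n). With n = 18, t(0.95; 17 df) = 1.740. At SD 0.6 the half-width is 1.740 × 0.6/4.243 = 0.246, so the ratio runs from 0.508 to 0.831, a change of -49% to -17%. At SD 0.4 the interval is -45% to -23%, and at SD 0.8 it is -53% to -10%.

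**Covariance parameters**

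An unstructured matrix needs k(k+1)/2 parameters: 6 for three visits and 28 for seven.

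**The case against.** A reader might infer that the SAP has definitely dropped the model and that no interval will exist. The documents do not support that. SAP 5.3.3 makes a general statement in favour of MMRM with 90% intervals. SAP 6.1.1.2 plans a covariate-adjusted model of UPCR change at Week 13 and at every study week. Section 5.3.4, some sensitivity bullets and the example code are not visible, and Appendix 1.1 is keyed mainly to the interim analyses and is visibly incomplete. What stands is a conflict: 6.2.1 does not call on 5.3.3, and the 6.1.1.2 item is a sensitivity analysis of the primary endpoint that the SAP itself expects may not converge.

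A reader might also infer that patients doing badly leave first. The SAP change log mentions discontinuations but gives no number or reason. Protocol 6.4 keeps subjects who stop treatment in follow-up, so stopping drug is not the same as losing UPCR data. Outcome-related dropout is a possibility here, not a finding. Nor is UPCR time course the only efficacy question that the extension serves, because eGFR beyond Week 13 is one too.

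The FAS requires subjects to "have at least one post-baseline measurement of UPCR based on 24-hour urine collection", so a subject with only a Week 2 value is in the FAS but not in the primary model. That is a separate matter and does not distort the model at Weeks 5, 9 and 13.

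Further points reduce the stakes. The study is open-label and non-pivotal, and the decision probabilities use Week 13 only. Individual profiles are plotted to Week 33. A rough interval can be worked out from n, geometric mean and geometric CV, though it would still be observed-case. Protocol Section 9 lets the SAP modify secondary analyses, so the departure is not a breach in itself.

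**Conclusion.** The concern holds as an inconsistency. The SAP section that governs the secondary UPCR endpoint gives observed-case summaries without intervals for Week 2 and the visits after Week 13. Protocol 9.2.2 promises a model, and SAP 5.3.3 points the same way as the protocol. Weeks 5 and 9 keep model-based 90% intervals through the primary MMRM, and the Week 13 primary result is not touched.

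The possible overstatement of the Week 25 reduction is about 2 to 14 percentage points under the assumed 10% to 30% outcome-related dropout, and nothing if dropout is unrelated to UPCR. These figures show direction and rough scale. They are not estimates for this trial. The lack of a planned interval in 6.2.1 does not depend on any of these assumptions.

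**What to change.** In SAP 6.2.1, replace the cross-reference with a stated analysis:
- Log-scale change from baseline in 24-hour UPCR at Weeks 2, 5, 9, 13, 17, 21 and 25, analysed by MMRM per Section 5.3.3, with back-transformed LSMeans and 90% intervals by dose and week.
- A named structured covariance as the fallback, since 28 unstructured parameters are many for about 22 subjects per cohort.
- Subjects enrolled before Amendment 5 contribute through Week 13 only, so that values taken off drug are not mixed in. SAP 3.2.1 already draws this line for its tables.
- Weeks 17 to 25 reported only for doses with subjects treated beyond Week 13.
- The output added to Appendix 1.1.

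Keep the Week 5, 9 and 13 model as primary and the descriptive tables as support.

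The cost is one extra model on data already collected. It relies on missing at random, including for subjects whose data stop at Week 13 by design when a dose mixes the two enrolment periods. The structured covariance may well be needed.

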6.2.3. Pharmacokinetics Analysis

The PK concentration population is defined as all enrolled subjects who received at least one dose of PF-06730512 and have at least 1 measurable concentration.

6.2.3.1. Serum and urine PK concentrations

Presentations for PF-06730512 concentrations for subjects in the Concentration Analysis Set (as defined in Section 4.4.1) will include:

- A listing of all concentrations sorted by dose level, subject ID, day, nominal time post-dose, actual times, and whether a subject was enrolled prior to or after protocol amendment 5. Deviations from the nominal time will be given in a separate listing.
- A summary of concentrations by dose level and cohort, day, nominal time postdose, and enrollment prior to or after protocol amendment 5, where the set of statistics will include n, mean, median, standard deviation, coefficient of variation (cv%), minimum, maximum and the number of concentrations above the lower limit of quantification;
- Median concentrations time plots for timepoints
 - up to Week 13 predose (on both linear and semi-log scales) against nominal time post-dose by dose (all dose levels on the same plot per scale)
 - up to Week 13 predose (on both linear and semi-log scales) against nominal time post-dose by dose and 'Baseline Nephrotic Range Proteinuria' (see [REDACTED])

- Section 6.4; all dose levels and subgroups on the same plot per scale, using different line types to distinguish ‘non-nephrotic’ and ‘nephrotic’ range proteinuria at baseline)
- from Week 13 predose to last follow-up visit (on both linear and semi-log scales) against nominal time post-dose by dose and enrollment prior to or after protocol amendment 5 (all dose levels on the same plot per scale). Enrollment prior to, and after protocol amendment 5 will be distinguished with different line styles and/or symbols (e.g., solid vs dashed line)
 - Mean concentrations time plots for timepoints
 - up to Week 13 predose (on both linear and semi-log scales) against nominal time post-dose by dose (all dose levels on the same plot per scale)
 - up to Week 13 predose (on both linear and semi-log scales) against nominal time post-dose by dose and ‘Baseline Nephrotic Range Proteinuria’ (see Section 6.4; all dose levels and subgroups on the same plot per scale, using different line types to distinguish ‘non-nephrotic’ and ‘nephrotic’ range proteinuria at baseline)
 - from Week 13 predose to last follow-up visit (on both linear and semi-log scales) against nominal time post-dose by dose and enrollment prior to or after protocol amendment 5 (all dose levels on the same plot per scale). Enrollment prior to, and after protocol amendment 5 will be distinguished with different line styles and/or symbols (e.g., solid vs dashed line)
 - Individual concentration time plots by dose level and cohort (on both linear and semilog scales) against actual time post-dose (there will be separate spaghetti plots for each dose per scale). To distinguish between subjects enrolled before and after amendment 5, assessments from each individual’s Follow-up Period will be interpolated with a different line style (e.g., a dashed line) than assessments from the Investigational Treatment Period.

The length of time used for the x-axes of these plots will be decided on review of the data, and will depend on how long PF-06730512 concentration is quantifiable above the limit of quantification in the matrix.

For summary statistics, median and mean plots by sampling time, the nominal PK sampling time will be used, for individual subject plots by time, the actual PK sampling time will be used.

6.2.3.2. Serum PK parameters

The serum PK parameters detailed in Section 3.2.3 will be listed and summarized descriptively by dose level, as data permit. Missing values will be handled as detailed in

Section 5.4.1. Each PK parameter will be summarized by dose level and will include the set of summary statistics as specified in Table 4.

[figure not shown]
Table 4. Serum PK Parameters to be Summarized Descriptively by Dose Level

Parameter	Summary Statistics
Day 1 and Day 71 AUC _{tau} , AUC _{tau} (dn), C _{max} , C _{max} (dn)	N, arithmetic mean, median, SD, %CV, minimum, maximum, geometric mean and geometric %CV
CL, Vss	
Day 1 and Day 71 T _{max}	N, median, minimum, maximum
t _{1/2}	N, arithmetic mean, median, SD, %CV, minimum, maximum

CCI

CCI

CCI

CCI

6.5. Baseline and Other Summaries and Analyses

6.5.1. Study Conduct and Subject Disposition

Subject evaluation groups will show subject disposition and will show which subjects were analysed for efficacy (FAS) and safety (SAS). Frequency counts and percentages will be supplied for subject discontinuation(s) by dose.

6.5.2. Demographic Data

A summary of demographic data will be based on the respective SAS and provided for age, race, weight, body mass index and height. Baseline disease characteristics (duration of FSGS diagnosis, type of FSGS subtype and disease recurrence type) will be summarized in a further separate table.

Each will be summarized by sex at birth and 'All Subjects' for each dose separately.

6.5.3. Concomitant and Prior Medications

All prior and concomitant medication(s) will be reported and will be generated from the SAS. Three tables will be reported, one listing all concomitant medication(s), 1 restricted to treatments for FSGS and 1 restricted to antihypertensives and diuretics only.

6.5.4. Discontinuations

Subject discontinuations, temporary discontinuations or dose reductions due to adverse events will be detailed and summarised by dose (if applicable) and will be based on the respective SAS.

